In the past century, measures have been increasingly implemented in the field of anesthesia to combat the incidence of preoperative and perioperative complications. However, management of a difficult airway in perioperative settings, emergency rooms, critical care units, and pre-hospital settings remains challenging. Due to this, suboptimal outcomes associated with management of patients with a difficult airway can occur, particularly if the difficulty is unexpected. A difficult airway can be due to difficult mask ventilation, difficult ventilation with supraglottic airway, and difficult tracheal intubation. The most severe scenario of difficult airway is when a “cannot intubate and cannot ventilate” scenario is encountered, the patient’s oxygenation is significantly compromised, and the return of effective spontaneous breathing is not possible in a timely fashion. The recommended default rescue measure is invasive airway access(1, 2) However, a large-scale study demonstrated that the success rate of invasive airway access performed by experienced anesthesiologists is only about 35%.(3) Therefore, the search for an alternative way to save the lives of patients with difficult airways is an unmet demand and requires urgent attention and effort.

Management of a difficult airway has focused on the improvement of ventilation and intubation. Resumption of spontaneous breathing is the last option before invasive airway access is attempted. Previous reports indicate that the return of effective spontaneous breathing is unlikely in most patients if a “cannot intubate and cannot ventilate” event is encountered, due to the limits of safe apnea time.(4) This is particularly true if succinylcholine is used, as there is no reversal agent for succinylcholine-induced muscle paralysis. The time of muscle tone recovery to 50% of the baseline value after a single bolus of succinylcholine with induction dose (1 mg/kg) can reach 8.5 minutes on average.(4)

Recently, sugammadex was made available to reverse the muscle paralysis achieved with vecuronium and rocuronium.(5, 6) Complete reversal can be obtained within 2 minutes if an adequate dose of sugammadex is administered after a routine induction dose of rocuronium (0.6 mg/kg). The availability of sugammadex has the potential to change current anesthetic guidelines. However, its advantages have not been systemically assessed.

In a classic anesthetic induction, a sedative-hypnotic medication such as propofol is administered. After an IV bolus of propofol (1-2 mg/kg) is given, it reaches its peak level in the brain in about 1 minute and quickly declines.(7) For classic induction (CI), a bolus of neuromuscular blocking drug (NMBD), commonly rocuronium (0.6 mg/kg), is administered after the provider attempts mask ventilation and proves its effectiveness. However, new recommendations state that a paralytic agent should be administered if mask ventilation is proven difficult or impossible.¹ Therefore, attempted mask ventilation wastes time if a “cannot ventilate and cannot intubate” scenario is encountered. In addition, classic teaching has two more major disadvantages. First, the majority of “cannot intubate and cannot ventilate” situations are not anticipated. Second, most aspiration events that occur during induction are with mask ventilation. Therefore, the classic airway management of an unanticipated difficult airway is not optimized, particularly in terms of utilizing apnea oxygenation time.

A “time principle induction” (TPI) has been tested by an administration of a non-depolarizing neuromuscular-blocking agent before a sedative-hypnotic is given in the operating room setting.(8-13) It is also tested in an emergency room setting and has been proven that there are no differences in intubating conditions and the success rate of first attempted intubation between the two approaches, CI and TPI.(14) However, even with the

non-inferiority results of TPI vs. CI, the sample size of the previous studies were small. More importantly, the non-depolarizing paralytic agent was given 20 seconds before administering a sedative,(8) or the sedative was given at the onset of clinically observed muscle weakness.(9) (10) (11) (12) (13) Therefore, patient awareness of muscle paralysis before a loss of consciousness and post-operative recall is of great concern, although previous studies have not demonstrated whether this occurs.

The TPI can be modified – Modified Time Principle Induction (MTPI) – by administering a sedative and a neuromuscular blocking agent nearly simultaneously to minimize the likelihood of awareness of muscle paralysis before a loss of consciousness (Figure 1). In CI, a propofol bolus (1-2 mg/kg) will typically result in apnea in about 60 seconds. Attempted mask ventilation, followed by administration of NMBD, will take over 3 minutes, as it takes about 3 minutes to reach maximal muscle paralysis. If an intubation attempt is unsuccessful followed by an unsuccessful supraglottic airway (SGA) insertion, this will likely encompass an additional two minutes of time. If sugammadex (16 mg/kg) is given with return of adequate spontaneous breathing occurring 2 minutes after administration, the total apnea time will be 8 minutes. In a MTPI, patients would receive a non-depolarizing NMBD first, like rocuronium (0.6 mg/kg), immediately followed by a sedative-hypnotic, like propofol 1-2 mg/kg, without waiting for the onset of muscle weakness. Once apnea occurs, attempted intubation starts. If the intubation is not successful, it is followed by attempted mask ventilation, and then SGA ventilation (each step takes 1 minute). If none of them are successful, sugammadex is given. A total of 5 minutes of apnea time is needed to regain adequate spontaneous breathing. The apnea oxygenation time is shortened by 3 minutes or by 43%. Therefore, the need for invasive airway management will likely be reduced. Since the

sedative-hypnotic and muscle relaxant are administered simultaneously, the awareness of paralysis before loss of consciousness is unlikely to occur.

[figure not shown]

Figure 1. Schematic demonstration of intubating conditions created by Classic Induction vs. Modified Time Principle Induction (MTPI) with propofol and rocuronium. Propofol concentration in plasma in the brain (red line). Rocuronium induced muscle paralysis for classic induction (blue solid line) and Modified Time Principle Induction (green solid line). Muscle paralysis reversal after Sugammadex after MTPI (green dotted line) and classic induction (blue dotted line).

2. Hypothesis

Intubation conditions between patients receiving MTPI and CI are comparable. We will test this hypothesis by comparing time to intubation between the two techniques.

3. Specific aims

- 3.1 To assess and compare the conditions for tracheal intubation obtained with MTPI and that obtained with CI.
- 3.2. To compare the efficiency of tracheal intubation with the two induction techniques.
- 3.3. To determine the rate of awareness during induction and post-operative recall of muscle weakness.

4. Patient enrollment

This study will be carried out in the main operating rooms at Memorial Hermann Hospital in the Texas Medical Center (TMC). The study team will approach the patients in the respective preoperative holding area after reviewing their medical records to determine eligibility. Once the study team believes that a particular patient is eligible to participate in the study, the study team will provide that patient with detailed information about the study and obtain informed consent from the patient.

4.1. Inclusion criteria:

- I. 18 or older years of age
- II. BMI $>30 \text{ kg/M}^2$ or Mallampati class III or IV
- III. Requiring general anesthesia and endotracheal intubation

4.2. Exclusion criteria:

- I. Acute and chronic respiratory disorders, including COPD and asthma
- II. ASA physical status classification $> \text{III}$
- III. Emergency surgery
- IV. Induction requiring cricoid pressure

- V. Patients requiring awake intubation
- VI. Pregnant women
- VII. Patients who require an induction dose of propofol less than 1 mg/kg
- VIII. Untreated ischemic heart disease
- IX. Contraindication to mask ventilation
- X. Allergy to propofol, rocuronium, or Sugammadex
- XI. Induction requiring succinylcholine

Randomization and Blinding

Patients will be randomly assigned to the MTPI group and the Classic Induction group (control) using an online randomization program (<https://www.randomizer.org/#randomize>). A concealed envelope will be opened prior to induction. A study arm specific handout of induction instructions will be handed to the anesthesia provider. Laryngoscopy will be done with C-MAC and the entire laryngoscopy and entire intubation procedure will be recorded and saved. Study team members converting the video recorded data to digital data will be blind to the interventions. Once the study is completed and the digital data is collected, the study team members will be unblinded.

5. Outcomes

5.1 Primary outcome: The time between laryngoscope insertion into mouth and the onset of ventilation after tracheal intubation with MTPI vs. CI as visualized with C-MAC

5.2 Secondary outcomes:

5.2.1 The success rate of first attempted tracheal intubation, number of attempts, and failed intubation.

- 5.2.2 The best glottic view
- 5.2.3 Provider determination of intubating conditions, based on whether intubation was classified as “Not difficult” or “Difficult”
- 5.2.4 Vital signs during intubation including HR, BP, end-tidal CO₂, and SpO₂
- 5.2.5 Injury associated with intubation, including injury of teeth, lips, tongue, and pharyngeal bleed
- 5.2.6 Patients’ physical response during intubation, including moving and coughing
- 5.2.7 Post-operative survey in PACU and post-operative day #1 to assess awareness of muscle paralysis before loss of consciousness, sore throat, nausea, and vomiting, and overall satisfaction. Please refer to the post-operative survey form.
- 5.2.8 Recollection of pain on induction.

6. Study protocol

After providing informed consent, the subjects will receive premedication in the usual manner. Premedication typically includes 0-2 mg of IV midazolam at the discretion of the care team. Subjects will then be transported to the operating room and placed on the operating room table in the supine position with the head in the neutral position on a pillow. Operators who will perform endotracheal intubation are limited to an anesthesiology attending, anesthesiology residents who have performed greater than 75 endotracheal intubations, a CRNA or Anesthesia Assistant with working experience greater than 1 year.

Mask ventilation or supraglottic ventilation will be utilized if the first intubation attempt is not successful.

Standard monitors for general anesthesia will be applied, including ECG, blood pressure, pulse oximetry, and capnography. Pre-oxygenation via a plastic mask will be carried out with a flow rate of 10-liter min⁻¹ of 100% O₂ until the expired O₂ concentration reaches ≥80%. Randomization with random allocation of patients to a group and concealment of treatment from the patient and intubation scorer is carried out once informed consent is signed. Patients from both study groups will receive 1 mg/kg of lidocaine intravenously, followed by an opioid such as fentanyl (1-2 mcg/kg), prior to administration of induction drugs. Patients assigned to MTPI will then be given rocuronium (0.6mg/kg), followed by propofol intravenously as a single bolus within 10 seconds. A typical propofol bolus for induction ranges from 1-2mg/kg, depending on the patient's age, medical history, and co-morbidities. Propofol dosing will be at the discretion of the care team. Patients will count down from one hundred. Once apnea occurs, as indicated by a lack of respiratory effort, the eyes will be taped, and intubation with C-MAC (Karl Storz 8403ZX, Tuttlingen, Germany) is initiated. An additional attempt of intubation is defined as the re-insertion of the C-MAC or insertion of another type of laryngoscope. The documentation of the intubation is performed by the study team. The laryngoscopy is continuously recorded and saved. The study team member who views the video of intubation and scores the difficulty of intubation and the glottic view is blind to the interventions. Patients assigned to CI will be induced as per routine care using lidocaine 1 mg/kg, an opioid such a fentanyl (1-2 mcg/kg), propofol 1-2 mg/kg, and rocuronium 0.6 mg/kg, and the intubation will be performed with a C-MAC. Patients will also count down from one hundred. The medications used for induction of anesthesia in both

arms of the study are those used for routine anesthesia care. In both study arms, dosing of medications for induction of anesthesia is standardized (lidocaine 1 mg/kg, fentanyl 1-2 mcg/kg, propofol 1-2 mg/kg, and rocuronium 0.6 mg/kg). The only difference between the two arms will be the timing of the medication administration, and the order in which medications are administered. The documentation of induction and intubation will be the same as that of the MTPI group. Vital signs and other parameters will continuously be recorded in the intraoperative record. Emergence and extubation are not protocolized. Once the patient arrives in the PACU, the study team will assess the patient 30 min after arrival and attempt to conduct a post-operative survey (see PACU Patient Survey).

7. Data acquisition and analysis

All ventilatory settings and measured parameters displayed on the operating room ventilator (Datex Ohmeda AS/5, Helsinki, Finland), including expired tidal volume, flow waveforms, end-tidal carbon dioxide partial pressure, exhaled carbon dioxide waveforms, and vital signs displayed on the monitor will be recorded intra-operatively in the electronic medical record and video recorded from the time of pre-oxygenation and 5 minutes after intubation. Specific time points that will be collected are induction time, onset of apnea, beginning of intubation attempt, and time to successful intubation (identified by time between laryngoscope insertion into the mouth and the onset of ventilations after tracheal intubations with MTPI vs. CI with C-MAC).

8. Predicted outcome and its significance

The study team assumes that MTPI will be non-inferior to CI in the rate of 1st attempt tracheal intubation success. Additionally, we predict no significant difference in intubation time, glottic view, rate of successful intubation, rate/severity of injury associated with tracheal intubation, and the rates of awareness of muscle paralysis before loss of consciousness using the two different types of approaches. The study team predicts that MTPI will create similar intubating conditions compared to CI and will shorten the apnea time by 3 minutes (a reduction in apnea time by 37.5%) if a “cannot intubate and cannot ventilate” scenario is encountered and sugammadex rescue is used to reverse muscle paralysis. By shortening apnea time, we expect that MTPI would improve difficult airway management and therefore patient outcomes.

Positive outcomes expected from this study include increased efficiency in induction and intubation. Another benefit would be no longer needing to mask ventilate. Since 60% of aspiration occurs during mask ventilation, avoiding mask ventilation will significantly reduce aspiration rates. Also, a high dose (1.2 mg/kg) of rocuronium recommended for rapid sequence induction may not be needed. Furthermore, it is known that succinylcholine is associated with increased muscle aches, cardiac arrest, and mortality rates. The new method of modified time principle induction being done in this study may lead to a decreased need for succinylcholine as an option for muscle paralysis.

9. Sample Size Calculation

The primary outcome is time between laryngoscope insertion into mouth and the onset of ventilation after tracheal intubation in CI vs. MTPI as visualized with C-MAC. Among successful intubations, laryngoscopy time with a C-MAC averaged 46 seconds (95% CI, 40-

51).¹⁵ We assume the time required for tracheal intubation with the two induction approaches using a C-MAC is not significant if the time between the two approaches is smaller than 15 seconds. With 80% power at 0.05 significance, a total sample size is 130 patients, with 65 patients in each arm. To account for a drop rate of 15%, we will enroll a total of 154 patients.

10. Risk Assessment

10.1. Potential complications associated with induction and intubation are expected to be the same between the two groups. In another words, this study would be unlikely to add risk or reduce the existing potential risk of induction and intubation.

10.2. Adverse effects of medications: Propofol and fentanyl are routinely used for anesthesia care. We will exclude the patients who are allergic to these two medications. Midazolam is routinely used as pre-medication. Any risk associated with these three medications will not be altered due to the study. All other medications will not be restricted to use for patient care including antiemetics.

10.3. Patient awareness of muscle weakness before a loss of consciousness is a potential risk of the study. However, previous studies using a time principle induction have not demonstrated this in both the operating room and emergency room settings. Therefore, we do not anticipate any increased risks of awareness of muscle weakness in the study group when compared to the control group.

11. Data Safety Monitoring

11.1. A data safety monitor will review the trial protocol and the accumulated data on an ongoing basis for the duration of the trial. This individual will be monitoring the

benefits and risks to the participants of the trial in order to protect patient safety, credibility of the trial and validity of the study results.

- 11.2. The data safety monitor will be unaffiliated with the study and will have no financial, scientific, or other conflict of interest with the trial. The data safety monitor will have experience in the proper conduct of clinical trials and statistical knowledge in order to evaluate the results of the data.
- 11.3. The data safety monitor will perform data reviews at 30, 60, 90, 120, and 143 patients, or sooner if indicated.
- 11.4. Specific roles of the data safety monitor include oversight and analysis of study data to ensure continuing safety of trial participants, efficacy of the study intervention, and data integrity. By reviewing the data as it accumulates, the data monitor can identify significant trends or issues, and provide recommendations for changes in the study as needed.

12. Reporting of Adverse Events or Unanticipated Problems involving Risk to Participants or others

The study team does not anticipate increased risk of intraoperative events or other complications associated with this study as compared with routine care. Any adverse events and complications occurring in either group will be reported in the Data Collection Sheet.

- 12.1. Adverse events (AE) will be obtained and documented by the investigators performing data collection and by questioning or examining the patient. All new complaints and symptoms (i.e., those not existing before the signing of informed consent) will be recorded on the AE CRF.

12.2. AE's will be characterized in terms of their start and stop dates, start and stop times, intensity, action taken, relationship to research study, subject outcome, and whether the AE led to an SAE.

12.3. The study team will perform a review of adverse events after enrollment of 20 subjects.

13. Privacy/Confidentiality Issues

Measures will be taken to prevent lapses in confidentiality from occurring. Only key study personnel will have access to identified information. Exported and extrapolated data will be stored on a password protected UTHealth computer that only key study personnel can access. Any paper records will be kept in a drawer with a lock within [name] office.

14. Follow-up and Record Retention

Records will be kept through the HIPAA-compliant servers of McGovern Medical School. All the documents will be kept in [name] office in the drawer with a lock. All research tests will be performed under a code that protects the identity of the participants. Records of experimental procedures will be kept at least 6 years following the publication of the study results. At that time, research data will be destroyed.

15. Milestone of the study

- August 15, 2022. Approval of IRB application
- August 16, 2022. Initiation of the study
- August 29, 2022. Completion of the study – the first 10 patients

- November 21, 2022. Completion of the study – first 100 patients
- January 16, 2025. Completion of the study total 154 patients

16. Cost and resources

All the equipment needed for the study is for routine anesthesia care and is available in the operating room. Participation in this study will not cost more than that of ordinary care. Since this study imposes minimal risk, and little effort on the participants is needed, the participants will not be compensated and will be discussed at the time when consent is obtained. [name] will provide an encrypted laptop computer for the study team.

17. References

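### The hypothesis of comparable intubating conditions is to be tested by time to intubation, while the protocol's own measures of conditions have no stated role in the conclusion

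*Combined protocol and SAP*

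**What the plan says.** Section 2 (Hypothesis) reads "Intubation conditions between patients receiving MTPI and CI are comparable", followed by "We will test this hypothesis by comparing time to intubation between the two techniques". Section 3 keeps two questions apart. Aim 3.1 is "To assess and compare the conditions for tracheal intubation obtained with MTPI and that obtained with CI". Aim 3.2 is "To compare the efficiency of tracheal intubation with the two induction techniques".

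Section 5.1 gives one primary outcome: "Primary outcome: The time between laryngoscope insertion into mouth and the onset of ventilation after tracheal intubation with MTPI vs. CI". The condition measures appear elsewhere:

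- 5.2.3: the provider's rating of the intubation as difficult or not difficult.
- 5.2.6: "Patients’ physical response during intubation, including moving and coughing".
- Appendix 1: a 0 to 3 score built on jaw relaxation, paralysis, vocal cords, movement and coughing, with 0 for failure to intubate. It is tabulated by arm but is not listed among the Section 5 outcomes, and no assessor is named.

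Section 9 bases the sample size on time. It assumes that the difference "is not significant if the time between the two approaches is smaller than 15 seconds", and names no test or confidence-limit criterion. Section 8 returns to conditions: "The study team predicts that MTPI will create similar intubating conditions compared to CI". It gives no criterion for that statement either.

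**The concern.** The hypothesis is about one thing and its stated test measures another. A patient who coughs, moves or has a firm jaw may still be intubated with a videolaryngoscope in close to ordinary time. If only some patients are affected, and each is slowed modestly, the mean time moves little.

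The mismatch falls where the arms could plausibly differ. In MTPI, laryngoscopy starts at apnea. The background section puts apnea at about 60 seconds after propofol (stated for CI) and maximal paralysis at about 3 minutes. The primary clock starts only at laryngoscope insertion. Incomplete relaxation would therefore show first in the condition measures, and in time only as far as it slows the procedure.

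At stake is the main claim. Followed as written, the plan could support a report of comparable conditions on a time result while the trial's own condition data point the other way. Nothing in the plan says which would prevail.

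**Working it through.** **1. The plan's own figure.** Section 9 gives 65 per arm, 15 s, 80% power and 0.05 significance, but no SD, so 130 can be neither confirmed nor refuted. Solving backwards with a two-sample t-test (two-sided 0.05), 65 per arm has 80% power at a standardised difference of 0.4952:

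- SD = 15 / 0.4952 = 30.3 s
- SE of the difference = 30.3 × √(2/65) = 5.31 s

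Other readings of the same line, by normal approximation, give 29.2 s (two one-sided tests at 0.05) to 34.4 s (non-inferiority, one-sided 0.05). The dropout step does reproduce: 65 / 0.85 = 76.5, rounded up to 77 per arm, or 154.

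**2. Dilution.** If an excess proportion *e* of MTPI patients has poor conditions and each takes *X* seconds longer, the mean shifts by *e* × *X*. Neither value is in the documents. I assume 10% in CI and 40% in MTPI (*e* = 0.30):

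- *X* = 10 s: shift 3 s
- *X* = 20 s: shift 6 s
- *X* = 30 s: shift 9 s

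All lie below 15 s.

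**3. Chance of a favourable time result.** With no rule named, I take three readings, where δ is the true shift and SE = 5.31 s:

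- A: observed difference within ±15 s: Φ((15 − δ)/SE) − Φ((−15 − δ)/SE)
- B: two-sided t-test not significant at 0.05 (noncentral t, 128 df)
- C: upper 95% limit below 15 s: Φ((15 − δ)/SE − 1.96)

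| δ | A | B | C |
|---|---|---|---|
| 0 s | 99.5% | 95% | 81% |
| 3 s | 98.8% | 91% | 62% |
| 6 s | 95.5% | 80% | 40% |
| 9 s | 87.1% | 61% | 20% |

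Over SDs of 29.2 to 34.4 s, a 6 s shift gives 78% to 83% under B and 42% to 32% under C.

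**4. What the condition outcomes could show.** Fisher exact power with 65 per arm, two-sided 0.05, assumed rates:

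| CI vs MTPI | Power |
|---|---|
| 10% vs 40% | 98% |
| 10% vs 30% | 78% |
| 10% vs 20% | 28% |
| 5% vs 15% | 37% |

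A large excess would be seen directly. A doubling from 10% to 20% would usually not reach significance, so a non-significant condition outcome is not evidence of comparability.

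**The case against.** **Time is a defensible primary outcome.** It is objective and is read from video by blinded staff. The provider works from arm-specific instructions, so the 5.2.3 rating is unblinded. This stands: the point is not that time should cease to be primary, but that it should not carry a claim about conditions.

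**The condition data are planned.** Outcomes 5.2.3 and 5.2.6 and the Appendix 1 table would be visible beside the time result, as would glottic view and first-attempt success. A reader might infer that the trial ignores conditions; the documents do not support that. What is missing is any statement of how these data bear on the conclusion.

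**No 15-second decision rule exists.** A reader might infer that the plan declares conditions comparable whenever the time difference is under 15 s, and so take the 99/96/87% figures as the plan's error rate. Section 9 uses 15 s only as a sample-size assumption. Under the confidence-limit reading the pass rates fall to 62/40/20%.

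**Time is not blind to conditions.** Under that reading a 9 s shift fails about 80% of the time. Longer delays also count: the background section allots 1 minute to each step after an unsuccessful intubation. If an affected patient lost 60 s, an excess of 15 / 60 = 25 percentage points would move the mean by the full 15 s. The 10 to 30 s range does not represent such cases.

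**Conclusion.** The concern holds as a mismatch between hypothesis and test. Section 2 lets time test a claim about conditions, the protocol itself treats the two as separate aims, and no condition outcome has a stated role in the conclusion. This rests on the text and needs no assumption.

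Its size does rest on assumptions. With 30 percentage points more poor conditions and 10 to 30 s added per affected patient, the mean shift is 3 to 9 s. The chance of a favourable time result then runs from 99% down to 20%, depending on the delay and on the rule eventually applied. The SD is back-solved, and the rates and delays are illustrative. A reader might also infer that MTPI does worsen conditions. The documents give a reason to look, but no data showing it.

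**What to change.** **Section 2.** State the hypothesis that the primary outcome tests: *Time to intubation with MTPI is comparable to that with CI (within 15 s).* Remove the sentence that makes time the test of conditions.

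**Sections 5 and 8.** Base any statement of similar intubating conditions on the condition outcomes:

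- moving or coughing (5.2.6);
- provider-rated difficulty (5.2.3), noting that the provider is not blinded;
- the Appendix 1 score, added as a secondary outcome with a prespecified cut (for example 0–1 versus 2–3) and a stated assessor. The blinded video reader in Section 6 is described as scoring difficulty and glottic view, so it should not be assumed that this score comes from the video.

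Report each as an MTPI minus CI risk difference with a 95% confidence interval beside the time result. If an interval shows worse conditions with MTPI, do not describe conditions as comparable, whatever the time result. If the difference is merely non-significant, call it inconclusive and give the interval.

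**Cost.** Wording in three sections, one added secondary outcome and three risk differences. No patients or procedures are added; the assessor for the Appendix 1 score must be settled. The downside is that a favourable time result alone will support a narrower claim, about time or efficiency.

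### Propofol and opioid doses are chosen within two-fold ranges by a provider who can already know the arm, so the plan does not secure its claim that only timing and order differ

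*Combined protocol and SAP*

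**What the plan says.** The unnumbered section on randomization and blinding sets out when the arm becomes known: "A concealed envelope will be opened prior to induction". It then says who learns it: "A study arm specific handout of induction instructions will be handed to the anesthesia provider". Section 6 describes treatment as concealed from the patient and the intubation scorer; the provider giving the drugs is not listed.

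On dosing, Section 6 fixes lidocaine at 1 mg/kg and rocuronium at 0.6 mg/kg. Propofol has a typical range of 1-2 mg/kg that depends on age, history and co-morbidities, and "Propofol dosing will be at the discretion of the care team". Lidocaine is "followed by an opioid such as fentanyl (1-2 mcg/kg), prior to administration of induction drugs". The classic induction (CI) arm follows routine care with the same ranges. Premedication is open as well: "Premedication typically includes 0-2 mg of IV midazolam at the discretion of the care team".

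Section 6 then summarizes: "In both study arms, dosing of medications for induction of anesthesia is standardized", followed by the same fixed doses and ranges, and "The only difference between the two arms will be the timing of the medication administration", together with the order of administration.

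**The concern.** A drug that is chosen over a two-fold range by someone who knows the arm is not held equal by randomization. Randomization balances the patients' characteristics. It does not balance decisions made after the allocation is seen.

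The documents supply a reason to dose by arm in each direction. Section 10.3 says "Patient awareness of muscle weakness before a loss of consciousness is a potential risk of the study". It expects no increase over control, but a provider about to give rocuronium before propofol could still choose to sedate more in the modified time principle induction (MTPI) arm. In the other direction, the Background says propofol peaks in the brain at about one minute and then falls quickly, and puts the CI sequence of mask ventilation and paralysis at over three minutes. That could prompt more propofol in CI.

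The outcomes at stake are secondary but include the main safety question about the technique: awareness and recall (Aim 3.3, outcome 5.2.7). Movement and coughing (5.2.6) and heart rate and blood pressure (5.2.4) also plausibly respond to hypnotic and opioid dose. If the arms differ in dose, a difference or a lack of difference on these outcomes cannot be attributed to drug order. For recall, extra sedation in MTPI would push toward the absence of a difference that Section 8 predicts. For the other outcomes the direction is uncertain. Blinded video scoring does not help, because the bias would enter when treatment is delivered.

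**Working it through.** **What is fixed and what is open (Section 6)**

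| Drug | Dose rule | Fixed before the arm is known? |
|---|---|---|
| Lidocaine | 1 mg/kg | Yes, by protocol |
| Rocuronium | 0.6 mg/kg | Yes, by protocol |
| Propofol | 1-2 mg/kg, typical, care-team discretion | No |
| Opioid | Agent open; 1-2 mcg/kg if fentanyl | Not required |
| Midazolam | 0-2 mg, care-team discretion | Not required |

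The arm is certainly known when propofol is given, since the drug order is the intervention. It can be known when the opioid is given, which Section 6 lists among the induction medications. Midazolam is not in the sentence about standardized dosing. It comes earlier, before transport to the operating room, but the protocol says only that the envelope is opened before induction, not that this follows premedication.

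**Inputs for the arithmetic.** Section 9 gives 65 patients per arm. This is taken as stated and not disputed; its inflation for 15% dropout reproduces: 65/0.85 = 76.5, rounded up to 77, and 2 × 77 = 154. The documents give no SD for dose, so it is assumed:

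- central value: doses spread uniformly over 1-2 mg/kg, SD = 1/√12 = 0.289;
- low value: SD 0.15;
- high value: SD 0.50, the maximum within the range, with every dose at 1 or 2 mg/kg.

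**Imbalance expected by chance.** If dose depends only on patient factors, the arm means differ by sampling error alone:

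- SE of the difference = SD × √(2/65) = SD × 0.1754
- 95% limit = 1.96 × SE
- gap detectable with 80% power at two-sided 0.05 = (1.96 + 0.842) × SE

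| Assumed SD (mg/kg) | SE | 95% chance limit | Gap detected with 80% power |
|---|---|---|---|
| 0.15 | 0.0263 | 0.052 | 0.074 |
| 0.289 | 0.0506 | 0.099 | 0.142 |
| 0.50 | 0.0877 | 0.172 | 0.246 |

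Dosing by arm, in contrast, is bounded only by the 1 mg/kg width of the range. That is an outer limit and not a forecast. For fentanyl the same figures apply in mcg/kg, provided that fentanyl is the agent used and its spread is the same.

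**Weight of one recall report.** 1/65 = 1.54 percentage points on an arm's rate. This shows how few events could alter the comparison; it is not an estimate of bias.

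**The case against.** The strongest reply is that this is ordinary practice. Induction doses are individualized, the provider in a comparison of techniques cannot be blinded, and Section 6 ties propofol dose to patient factors that have nothing to do with the arm. The sentence on standardization lists the ranges it means, so a reader can see that it refers to common ranges. Nothing shows that providers will dose by arm. The suggested motives point in opposite directions, Section 10.3 expects no increase in awareness, and the plan reports that earlier timing-principle studies did not show it. A declared dose is not binding, and a table of given doses would already reveal a sizeable gap. The Data Collection Sheet is not reproduced and may already hold doses.

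Much of this stands. The documents show an opportunity, not a tendency, and the size of any effect is unknown. The midazolam point is the weakest, since premedication probably precedes the envelope in practice. Reading standardized as equal ranges is fair.

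It does not remove the point. Equal ranges are weaker than the claim that timing and order are the only difference, and patient-based dosing guidance does not stop knowledge of the arm from influencing the choice. A table of given doses could show a gap but could not separate a chance difference in patients from departures made once the arm was known. Intended doses recorded beforehand can.

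**Conclusion.** The concern holds. Propofol dose, and possibly opioid and midazolam dose, can be chosen with the arm known, and the plan contains no step that separates the choice from the allocation. Its statement about the only difference between arms is therefore stronger than its procedures support.

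The conclusion that the opportunity exists rests on the text alone. No bias is quantified, because the documents give neither a recall rate nor a dose effect, and none is claimed for the primary outcome. The calculation shows only that a dose table by arm would be informative: under the central assumption, a mean propofol gap much above 0.10 mg/kg would be hard to attribute to chance. The change is recommended because it protects the awareness comparison at very little cost; the trial's main analysis does not depend on it.

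**What to change.** In the randomization section and Section 6, keep the envelope sealed until:

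1. midazolam has been given or declined and its dose recorded; and
2. the care team has written down the intended propofol dose in mg/kg and the intended opioid and its dose.

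Then open the envelope. Record all doses actually given up to the onset of ventilation, tabulate intended and given doses by arm, and report awareness by midazolam use (yes/no) descriptively. Reword the Section 6 summary to say that the same dose ranges are permitted in both arms and that the planned difference is timing and order.

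The declaration should be easy to obtain: exclusion criterion VII removes patients who require less than 1 mg/kg of propofol, so the team must already consider the dose at eligibility.

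The cost is protocol wording, plus fields for intended and given doses if the Data Collection Sheet lacks them. The envelope is opened slightly later. The team may still depart from the declared dose for clinical reasons, but the departure would then be visible. No dose changes, and the sample size stays at 130 (154 enrolled).
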